### ***Study Population – Inclusion/Exclusion Criteria***

There are no definitive criteria for diagnosing DKA. Thus, using the criteria employed by Self et al. and the Diabetes Canada guidelines we will include ED patients  $\geq 18$  years with a clinical diagnosis and laboratory values consistent with DKA, including:

- plasma glucose concentration  $\geq 14$  mmol/L
- plasma bicarbonate concentration  $\leq 18$  mmol/L and/or blood pH  $\leq 7.30$
- calculated anion gap  $> 10$  mmol/L
- presence of ketones/beta-hydroxybutyrate in serum and/or urine

We will exclude patients who:

- Are initially seen at another ED and transferred to LHSC for care and/or admission
- Receive  $> 1$  L of IV fluid prior to enrolment (e.g. pre-hospital by EMS or while waiting to be seen) – this may cause study contamination
- Are initially enrolled due to clinical suspicion of DKA based on elevated point-of-care glucose, but ultimately do not meet clinical/laboratory criteria for DKA (e.g. “hyperglycemia” only)
- Have euglycemic DKA (generally those on SGLT-2 inhibitors)

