### ***Study Procedures***

#### **Screening, Consent, and Enrolment**

During weekday business hours (M-F 0700-1700), research assistants (RAs) will screen and identify eligible patients using our ED tracking board. They will approach the treating physician to confirm eligibility before discussing the study with the patient and seeking informed consent. Because the diagnosis of DKA requires laboratory confirmation, all patients with a point-of-care blood glucose confirming hyperglycemia ( $\geq 14$  mmol/L) will be approached for enrolment as a “possible DKA patient”. If the treating physician agrees that DKA is possible and IV fluid is indicated, study fluid will be administered per the randomization protocol after consent is obtained. If patients are initially enrolled but the physician ultimately confirms they do not meet DKA criteria, they will be excluded from the analysis. During evening and weekend hours, RAs

will be available on-call, however nighttime coverage (after 2300h) will not be feasible for this pilot. After hours (and in the event our processes are affected by a prolonged COVID-19 pandemic), treating physicians can directly enroll patients as there will be study posters to outline enrolment processes and physicians will receive email and in-person reminders on study recruitment. We will review daily ED visit logs to identify missed patients to screen for bias.

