We plan to conduct the full-scale trial at 6 ED sites over 2 years, which would require an average minimum recruitment of 86 participants per site (43 per site per year). Our research group has established relationships with these other Canadian EDs where we have previously conducted successful studies. If further sites are needed for recruitment, we will leverage the Network of Canadian Emergency Researchers (NCER).

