### ***Sample size for Pilot Trial***

For the full-scale trial, a minimum of 43 participants must be recruited annually per site on average. The LHSC Victoria Campus ED treats approximately 130 patients with DKA annually, based on our hospital's Decision Support data from the most recent fiscal year (Mar 1 2019 – Feb 29 2020).

DKA by Site	Patients
Victoria Hospital	130
(E1010) Type 1 DM with ketoacidosis	70
(E1110) Type 2 DM with ketoacidosis	51
(E1112) Type 2 DM with keto & lactic acidosis	1
(E1410) Unspecified DM with ketoacidosis	8

Based on our research team hours of coverage (0700-2300) and past data from ED presentation time of potentially eligible patients, we expect to approach at least 104 (80%) of eligible patients in the one-year pilot study period, and a minimum of 43 approached participants (41.3%) must be recruited to meet the feasibility target. According to data from similar past trials, we

anticipate being able to recruit at least 50% of approached patients (target sample size of 52 patients, 26 in each arm). With 104 patients approached per year, a 90% two-sided confidence interval around the anticipated recruitment rate will have a total width of 0.17, i.e. a lower limit of 0.415 and an upper limit of 0.585. Because the lower limit excludes the minimum feasibility target of 41.3%, we can be 90% confident that the future trial is feasible.

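### The statement of 90% confidence that the future trial is feasible does not follow from an interval drawn around an assumed recruitment rate

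*Combined protocol and SAP*

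**What the plan says.** All references are to the combined protocol and SAP.

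- *Primary Feasibility Outcome* makes the one-year recruitment rate the primary feasibility outcome. It defines neither numerator nor denominator.
- *Sample size for Full-Scale Trial* gives the source of the yearly target. Six sites over two years "which would require an average minimum recruitment of 86 participants per site (43 per site per year").
- *Sample size for Pilot Trial* starts from about 130 DKA-coded patients a year at the site and states "we expect to approach at least 104 (80%) of eligible patients in the one-year pilot study period". The criterion is that "a minimum of 43 approached participants (41.3%) must be recruited to meet the feasibility target". The anticipated rate is at least 50%, hence a target sample of 52. A two-sided 90% interval around that rate is given as 0.415 to 0.585, and the section ends: "Because the lower limit excludes the minimum feasibility target of 41.3%, we can be 90% confident that the future trial is feasible".
- *Screening, Consent, and Enrolment* has patients with a point-of-care glucose of 14 mmol/L or more approached as possible DKA. For research assistants the order is: "They will approach the treating physician to confirm eligibility before discussing the study with the patient and seeking informed consent". Once the physician agrees that DKA is possible and fluid is indicated, "study fluid will be administered per the randomization protocol after consent is obtained". Then: "If patients are initially enrolled but the physician ultimately confirms they do not meet DKA criteria, they will be excluded from the analysis".
- *Study Population – Inclusion/Exclusion Criteria* lists as an exclusion those enrolled on suspicion "but ultimately do not meet clinical/laboratory criteria for DKA".

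**The concern.** A confidence interval supports a statement about the true recruitment rate only when it is computed from observed data. Here nobody has yet been approached, and the centre of the interval is the planners' own expectation. Saying that its lower limit clears the target amounts to saying that 50% is far enough above 41.3%, given 104 patients, for the two to be told apart if exactly 50% is observed. That is a useful precision statement, but it is not 90% confidence in feasibility.

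The sentence attaches an assurance to the pilot's primary feasibility outcome that the design does not provide. A funder or ethics board could take it as the probability that the pilot will succeed, or as something the pilot will demonstrate.

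A smaller point concerns who counts. Patients are approached and may receive study fluid before DKA is confirmed, and those without DKA are later removed from the analysis. The text does not say outright whether they count towards the 43, or which patients form the denominator of the rate.

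**Working it through.** **Inputs** (*Sample size for Pilot Trial* unless stated): 130 DKA-coded patients a year; 80% approached; anticipated recruitment 50%; two-sided 90% interval; 516 participants, 6 sites and 2 years (*Sample size for Full-Scale Trial*).

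**1. Reproduce the plan's figures.**
- Approached: 0.80 × 130 = 104. Expected recruits: 0.50 × 104 = 52.
- Target: 516 / (6 × 2) = 43 per site-year; 43/104 = 0.4135.
- The exact (Clopper-Pearson) 90% limits for x of n are the 5th percentile of Beta(x, n − x + 1) and the 95th percentile of Beta(x + 1, n − x). For 52/104 they are 0.4154 and 0.5846, a width of 0.169. This matches the stated 0.415, 0.585 and 0.17.

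The lower limit clears the target by 0.4154 − 0.4135 = 0.0019, about 0.2 percentage points.

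**2. Which observed results would put the lower limit above the target, with 104 approached?**

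| Recruited of 104 | Exact 90% lower limit | Above 0.4135? |
|---|---|---|
| 43 | 0.332 (upper limit 0.499) | no |
| 51 | 0.406 | no |
| 52 | 0.415 | yes |

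The cut-off is 52. Wald and Wilson intervals give the same cut-off, so the choice of interval method does not matter. Assuming one recruit fewer, 51 instead of 52, would have reversed the protocol's sentence.

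**3. How often would that happen?** With X ~ Binomial(104, p):

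| True rate p | P(X ≥ 52): lower limit exceeds 41.3% | P(X ≥ 43): count target met | P(43 ≤ X ≤ 51): count met, interval includes 41.3% |
|---|---|---|---|
| 45% | 0.18 | 0.80 | 0.62 |
| 50% | 0.54 | 0.97 | 0.43 |
| 55% | 0.87 | 0.998 | 0.13 |

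If the anticipated 50% is exactly true, the pilot's own interval would exclude 41.3% with probability 0.54, not 0.90.

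**4. Sensitivity to the number approached.** The protocol gives 104 as a floor. Hold the target at 43 and the true rate at 50%, and compare the exact lower limit with 43/n. The probability that it exceeds 43/n is 0.54 at n = 104, 0.75 at n = 110 and about 0.91 at n = 120. The values 110 and 120 are assumed for illustration.

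**5. Who counts.** The 104 is 80% of DKA-coded cases described as eligible, and unconfirmed DKA is an exclusion, so the natural reading of 43 is patients with DKA. The approach under *Screening, Consent, and Enrolment* covers possible DKA, a wider group. Only if every enrolment were counted, 52 enrolled would contain fewer than 43 with DKA once 10 or more proved not to have it (52 − 10 = 42). The documents do not give that share.

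**The case against.** The strongest reply is that this is one loose sentence in a planning paragraph. The text itself places the interval around the anticipated rate, so the conditional basis is visible, and deleting the sentence would change no procedure, outcome or analysis. That is largely fair and limits the weight of the point. It does not make the sentence true.

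Three further objections stand in part.

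- **Floors.** Both 104 and 50% are stated as minimums, so 0.54 describes the floor case only. With more patients approached, or a higher true rate, the probability rises, as shown above. An interval around an assumed rate would still be no evidence.
- **Contradictory conclusions.** A reader might infer that 43 to 51 recruits would leave the pilot both passing and failing. The documents do not support this. The count is the only stated criterion and it would be met. The interval is never set as a pass rule, and one that includes 41.3% is inconclusive, not a finding of infeasibility.
- **Counting patients without DKA.** A reader might infer that the plan will pad the 43 with them, or that it contradicts itself. It does neither. The DKA-coded base, the reference to eligible patients and the exclusion criterion all point to DKA patients. What is missing is an explicit statement. Counting confirmed cases only is also a choice, since the 516 behind the 43 already carries a 10% attrition allowance, described as loss to follow-up. Whether that allowance covers post-enrolment exclusions is left open.

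**Conclusion.** The closing sentence of *Sample size for Pilot Trial* is wrong as written. The interval is correctly calculated and valid as planning precision, but it cannot yield 90% confidence of feasibility. With exactly 104 approached, a binomial model and a fixed target of 43, the data would place the exact 90% lower limit above 41.3% with probability 0.18, 0.54 and 0.87 at true rates of 45%, 50% and 55%.

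The fault lies in the confidence claim, not in the target. A reader might take the 0.54 as the chance that the pilot succeeds. It is not: the stated criterion of at least 43 is met with probability 0.97 at a true rate of 50%.

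The definition of who counts is a minor gap in detail. The 43 itself depends on the 516, whose derivation cites both a 40% and a 25% reduction and needs separate reconciliation.

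**What to change.** 1. Replace the closing sentence of *Sample size for Pilot Trial* with: *If 52 of 104 approached patients are recruited, the exact 90% CI will be 41.5% to 58.5%.*
2. Keep the count of at least 43 in one year as the feasibility criterion, subject to reconciling the 516. Report the 90% interval around the observed rate descriptively, not as a second pass/fail test.
3. As a minor clarification in *Primary Feasibility Outcome* and *Sample size for Pilot Trial*, say whether the 43 counts only randomised patients with confirmed DKA, and define the denominator of the recruitment rate to match.
4. A confirmed-DKA rate needs the DKA status of approached patients who were not enrolled. *Data Collection* covers enrolled patients only. Unless that is extended, report separately the count with confirmed DKA and the rate of all enrolled over all approached, together with the number enrolled and later found not to have DKA.

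**Cost.** Items 1 to 3 are wording. The confirmed-DKA count needs no new data, because bloodwork and diagnosis are already abstracted for enrolled patients. A matched confirmed-DKA rate would need added data on those not enrolled; the separate reporting in item 4 avoids this. The downside is that the stated assurance becomes less favourable.

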## **DATA COLLECTION**

Study data for each enrolled patient will be abstracted from the hospital's electronic medical records into the Lawson REDCap data storage platform. Study data will include minimal demographic information (e.g. sex, date of birth), the patient's medical history (e.g. comorbidities, medications), arrival ED information (e.g. CTAS, arrival vitals), hospital interventions (e.g. IV fluids administered), comprehensive bloodwork results, and discharge and outcome information (e.g. length of stay, intubation, diagnosis).

## **DATA ANALYSIS**

We will follow an intention-to-treat analysis. Descriptive statistics will be used to summarize patient characteristics. Chi-square tests with 95% confidence intervals will be used to examine differences in categorical variables between groups, and two-tailed unpaired t-tests will be used to compare continuous variables. For this pilot study, we have not planned an interim analysis, Data Safety Monitoring Board, or adjudication committee, but these will be developed for the full-scale trial. This trial will be registered with ClinicalTrials.gov.

## **RISKS**

Participation in this study is entirely voluntary. Patients may refuse to participate, refuse to answer any questions, or withdraw from the study at any time with no effect on their future care. Participants do not waive any legal rights by signing the consent form. They will receive a copy of the letter of information should they be willing to consent.

There are no anticipated risks to participating in this study, other than a low possibility of a privacy breach occurring with the data collected during this study. However, the study team will take all necessary precautions to prevent this from happening and will remove any personal identifiers from all data collection forms.

## **BENEFITS**

For participants who are randomized to the Ringer's Lactate Group, there is a possibility that they may benefit from this intervention. The hypothesized benefit from the administration of the IV Ringer's Lactate may include improved faster resolution of DKA than if IV normal saline was administered. However, there is no guarantee that participants will benefit personally from participating in this pilot study.

This study will contribute important knowledge regarding DKA treatment. This pilot study will directly inform us if a full-scale clinical trial evaluating the use of a Ringer's Lactate compared to normal saline as part of DKA care in the ED is possible.

## **ETHICS AND PRIVACY**

We are seeking approval from Western Health Sciences Research Ethics Board. Patient personal health information will be stored confidentially according to standard procedures protected by LHSC firewall. Any paper research records will be stored in a locked cabinet in a secure office at LHSC, and electronic records will be password-protected on Lawson REDCap data storage platform. The data will be viewed only by members of the research team. If the results of this study are published, patient name will not be used and no information that discloses your identity will be released or published. Any identifiable information will be stored separately from the data and will be assigned a unique study code stored separately on a master log. Data will be retained for a period of 15 years after publication in a secure place, after which time it will be destroyed in a secure manner (e.g. shredded or electronically destroyed).

Qualified representatives of the following organizations may look at the study records at the site where these records are held, for quality assurance (to check that the information collected for the study is correct and follows proper laws and guidelines).

Examples include:

- Representatives of Lawson Quality Assurance Education Program
- Representatives of the University of Western Ontario Health Sciences Research Ethics Board that oversees the ethical conduct of this study.

## **PLANS FOR DISSEMINATION OF FINDINGS**

We will present the results from our pilot trial at national and international emergency medicine and diabetes conferences and submit manuscripts including our study protocol and results to peer-reviewed journals for publication. Our overall findings will be communicated via stakeholder organizations (CAEP, NCER, Diabetes Canada, American Diabetes Association), with the goal of changing DKA management guidelines internationally, and will be communicated through medical news/blogs such as EMCases and [www.canadiem.org](http://www.canadiem.org).

## **CONFLICTS OF INTEREST**

This project is funded by the Internal Research Fund (2021-2022) at Lawson Health Research Institute. The study funder is not involved in the design of the study; will not be involved in the collection, analysis and interpretation of data; writing of the manuscript; and will not impose any restrictions regarding publication of the manuscript.
